17 peginterferon alfa when added to long-term nucleoside therapy in patients with chronic HBV
18 infection (both HBeAg-positive and -negative). We hypothesize that the extended pretreatment with
19 NUCs will modify the responsiveness to peginterferon. These effects will be studied by analyzing the
20 expression pattern of ISGs, the response of NK cells prior to and after peginterferon injection
21 resulting in improved transcriptional control of cccDNA, the induction of antibodies against HBe and
22 HBsAg and T cell responses.

23 Primary endpoints of this trial will be the changes in expression levels of ISG's, intrahepatic total HBV
24 DNA and cccDNA content, changes in NK cell effector cell function measured before and following a
25 single dose of peginterferon stratified by treatment response and the rates of HBeAg and HBsAg loss
26 and seroconversion in HBeAg positive patients, HBsAg loss and seroconversion rate in HBeAg
27 negative patients. Secondary endpoints will be the induction of HBV-specific memory T cell
28 responses. A post-hoc analysis will stratify response rates upon available viral genotype data and
29 duration of NUC therapy prior to study enrollment. Other secondary end-points will include changes
30 in quantitative HBeAg and HBsAg levels during therapy and safety of the combination regimen.
31 Serological response rates, qHBsAg kinetics and safety end-points will be compared to historical
32 controls of published multicenter randomized trials comparing the efficacy of peginterferon and
33 NUCs in eAg positive and negative HBV carriers

34

HYPOTHESIS

In patients with chronic hepatitis B infection, under long-term viral suppression maintained by NUCs treatment, peginterferon add-on therapy will result in a greater proportion of subjects achieving serological response compared to before peginterferon was added. We hypothesize that response to treatment will be accompanied by measurable changes in host-response gene transcription profile, immune cell activation and function, and quantitative viral biomarker levels.

SPECIFIC AIMS

1. To assess the changes in ISG profile and NK cell function after a single dose of peginterferon in patients receiving long-term NUCs with maintained viral suppression
2. To determine rates of HBeAg and HBsAg loss with or without seroconversion and induction of HBV-specific memory T cells to peginterferon add-on treatment in eAg positive and negative HBV carriers on long-term NUC treatment.

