3. To identify pre- and on-treatment predictors of serological response to peginterferon add-on/nucleos(t)ide combination therapy.
4. To determine if there are differences in epigenetic regulation of cccDNA between HBeAg positive and negative CHB at baseline and following a single dose of peginterferon treatment

PROTOCOL OVERVIEW

We intend to enroll a total of 60 patients with HBeAg positive (n=30) and HBeAg negative (n=30) chronic HBV infection, who have been on-treatment with one or more nucleos(t)ide analogues for at least 192 weeks prior to study enrollment with maintained viral suppression (HBV DNA level <100 IU/ml). After a thorough medical evaluation and liver biopsy, participants will receive therapy with subcutaneous injections of peginterferon-alpha 2a at a dose of 180mcg per week for a total of 24 weeks. A second liver biopsy will be performed 6 hours following the first peginterferon injection for the purpose of assessing ISGs, intrahepatic NK cell quantity and function and intrahepatic viral biomarker response patterns. Most interferon induced genes achieve maximal response in the liver and periphery within 4 hours, begin to decline by 8 hours, and return to baseline levels by 24 hours post-administration of interferon. Because peginterferon is slower to be absorbed we have selected the six hour rather than a four hour time point.[38]

1 Patients will be followed carefully on weeks 0, 2, 4, 8, 12 and 24 during treatment and at 12 week
2 intervals thereafter until 48 weeks post-treatment.
3 During study visits patients will be assessed for compliance with study medications, as well as the
4 development of any treatment related side effects and/or adverse reactions. In addition, blood will
5 be drawn periodically for the assessment of routine blood tests, quantitative viral biomarker levels,
6 serological response markers and immune cell functional status.
7

8 **INCLUSION/EXCLUSION CRITERIA** 9

10 **Inclusion criteria: HBeAg positive group**

- 11
- 12 1) Age >18 years and older, male or female.
- 13 2) Known serum HBsAg and HBeAg positivity at the time of screening.
- 14 3) Ongoing treatment with one or more NUCs for at least 192 weeks before study entry.
15 Subjects may have a brief interruption of treatment for medical reasons (e.g. breast feeding)
16 not to exceed 8 weeks and none within the 48 weeks before study entry.
- 17 4) HBV DNA levels <100 IU/mL, measured at least 12 months prior to, and upon enrollment to
18 the study.

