26 glucose, blood urine nitrogen, creatinine, uric acid, ALT, AST, LDH, CPK, Alkaline
27 Phosphatase, total and direct bilirubin, albumin, total protein), CBC (hematocrit, hemoglobin,
28 white blood cell count and differential, platelet count).
- 29 7) Females of child bearing potential: Pregnancy test
- 30 8) HBV DNA , qualitative and quantitative HBeAg, HBsAg, measurements
- 31 9) 30 mL of blood in heparinized green top tubes for NK and T cell analysis prior to PegIFN
32 injection and 30 mL of blood in heparinized green top tubes for NK and T cell analysis 6h
33 after PegIFN injection.
- 34 10) Blood sample for storage (10 mL of blood separated into serum and stored frozen in 0.5-1.0
35 mL aliquots)
- 36 11) Start peginterferon 180 ug SQ

1 12) Repeat liver biopsy 6 hours after first dose of peginterferon. Liver biopsy cut into four
 2 sections, one (at least 1.5 cm) placed in formalin for routine light microscopy and the other 3
 3 (.3cm, .5cm and 1 cm) placed in RNAlater and flash frozen in liquid nitrogen 24 hours later
 4 for RNA and protein analyses and flow cytometry.

5
 6
 7

8 Day1

9 1) 24h after the first PegIFN injection: 50 mL of blood in heparinized green top tubes for NK.
 10 This is the time point where we expect the maximal response of NK cells to PegIFN based on
 11 our previous studies [35, 36]
 12 2) Discharge from hospital

13

14

15 **Week 2,4, 8 and 12 (\pm 3 days):** Outpatient visit

16 Each outpatient visit will include assessment of compliance, adverse events reporting, vital signs,
 17 weight, symptoms evaluation, record of concomitant medications, drug dispensing

- 18 1) Symptom questionnaire
- 19 2) Visual analogue scale
- 20 3) Fatigue questionnaire (Promise 7) (week 2 only)
- 21 4) Chemistry 20 (sodium, chloride, potassium, bicarbonate, calcium, phosphate, magnesium,
 22 glucose, blood urine nitrogen, creatinine, uric acid, ALT, AST, LDH, CPK, Alkaline
 23 Phosphatase, total and direct bilirubin, albumin, total protein), CBC (hematocrit, hemoglobin,
 24 white blood cell count and differential, platelet count).
- 25 5) HBV DNA viral load, HBeAg, anti HBe, HBsAg and anti HBs measurment
- 26 6) Blood sample for storage (10 mL of blood separated into serum and plasma stored frozen in
 27 0.5-1.0 mL aliquots)
- 28 7) 50 mL of blood in heparinized green top tubes for NK and T cell analysis.
- 29 8) Females of child bearing potential: Pregnancy test
- 30 9) TSH and quantitative HBe and HBs antigen measurement at week 12.

31

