6 predictive factors associated with a favorable response to peginterferon therapy when added on to
7 long-term NUCs treatment, in patients with HBeAg positive and negative chronic HBV infection.

8

9 **Primary end-points**

10

- 11 1) The primary end-point for this study will be the change in level of ISG expression and NK cell
12 responses before and after 1st peginterferon injection in responders versus non-responders
13 to peginterferon add-on therapy.
- 14 2) Proportion of eAg positive patients showing eAg loss with or without seroconversion at end
15 of treatment and 24 and 48 weeks off therapy.
- 16 3) Proportion of eAg positive patients showing sAg loss with or without seroconversion at end
17 of treatment and 24 and 48 weeks off therapy
- 18 4) Proportion of eAg negative patients showing sAg loss with or without seroconversion at at
19 end of treatment and 24 and 48 weeks off therapy

20

21 **Secondary endpoints**

22

- 23 1. Level of qHBsAg decline at treatment week 12, at end of treatment and 24 and 48 weeks off
24 therapy, compared to pretreatment levels in eAg positive and negative patients
- 25 2. Level of qHBeAg decline at treatment week 12, at end of treatment and 24 and 48 weeks off
26 therapy, compared to pretreatment levels in eAg positive and negative patients
- 27 3. Correlation of qHBsAg levels at initial evaluation, week 12,24,36 and 48 with intrahepatic
28 pregenomic and cccDNA concentration before and after initiation of peginterferon in
29 responders versus non-responders to treatment.
- 30 4. Intrahepatic pregenomic and cccDNA concentration before and after starting treatment with
31 peginterferon.
- 32 5. Epigenetic alterations in HBeAg positive and negative patients following first 1st
33 peginterferon injection compared to pretreatment levels as measured by chromatin
34 immunoprecipitation (ChIp) assays

- 1 6. Frequency and functional activity of circulating and liver infiltrating, HBV-specific T-cells,
2 measured before and during treatment in responders versus non-responders to
3 peginterferon add-on therapy.
4

5 DOSE CHANGES 6

7 **Stopping peginterferon therapy:** 8

9 Add-on peginterferon will be discontinued early for any of the following reasons:

- 10 a) **Toxicity**- the dose of peginterferon will be modified or discontinued according to Table 1:
11 Peg-Interferon Alfa-2a Dose Modification Guidelines (see below).
12 b) **Withdrawal of informed consent** (subject's decision to withdraw for any reason.

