It is not possible to calculate power for the primary endpoints. We have calculated power for the secondary endpoints of the rates of HBeAg and HBsAg loss. Response rates in patients in both groups will be compared to historical controls of HBeAg positive and negative. It is assumed that if these patients were followed for an additional year without peginterferon, only 10% of the HBeAg positive patients would become HBeAg negative and 5% of the HBeAg negative patients would become HBsAg negative. A sample size of 29 HBeAg positive and 27 HBeAg negative patients will provide the study with a statistical power of 80% to detect a difference of 25% (35% versus 10% for HBeAg loss and 30% versus 5% for HBsAg loss). The sample size was increased to 30 patients in each arm to allow for withdrawals.

Variables to be analyzed in association with a serological response will include: baseline ALT and HBV DNA level, liver histology, HBV genotype, IL28B genotype, duration of NUC therapy, and ISG levels. Patients with missing data or who drop out of the study will be considered as treatment failures on an intention to treat basis. For comparison of means, Student's t-test will be used. All reported p-values will be 2-sided.

Demographics and Baseline Characteristics

The following will be summarized for treated subjects:

- Demographics: age, race, gender, geographic region, ethnicity;
- Disease characteristics at baseline: HBV DNA level, HBV genotype, IL28B SNP genotype and cirrhosis status, duration of NUC therapy;
- Physical measurements at baseline; height, weight, body mass index, hip and waist circumference;
- Laboratory tests at baseline;

Analysis plan

To address the primary hypothesis that ISG levels are related to virological response to peginterferon, the ISG analysis of the on treatment liver biopsy at 6 hours after the first dose of interferon will be correlated with off-peginterferon serological outcome (HBeAg loss/seroconversion and HBsAg loss). To address the hypothesis that ISG levels are related to HBsAg levels, the ISG analysis of the on treatment liver biopsy will be correlated with HBsAg levels at weeks 4, 12, 24.. The

1 analyses will be stratified by HBV genotype and duration of NUC therapy.

2

3 **Analysis methodology**

4

5 The analysis will be based on standard approaches to analysis of microarray data. Since the software
6 and approaches change frequently in this field, we will provide a broad outline of the approach

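### The ISG result is correlated with absolute HBsAg levels at weeks 4, 12 and 24 without the Day 0 value, so a pre-dose association cannot be told from a link to HBsAg decline

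*Combined protocol and SAP*

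**What the plan says.** Under STATISTICAL ANALYSIS, Analysis plan, the second analysis is introduced with the words "To address the hypothesis that ISG levels are related to HBsAg levels", and the method is that "the ISG analysis of the on treatment liver biopsy will be correlated with HBsAg levels at weeks 4, 12, 24". The only further structure is that the "analyses will be stratified by HBV genotype and duration of NUC therapy". Neither Day 0 HBsAg nor HBeAg status is listed, although the trial enrols 30 HBeAg-positive and 30 HBeAg-negative patients.

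Elsewhere the protocol thinks in terms of change. The HYPOTHESIS section expects that "response to treatment will be accompanied by measurable changes in host-response gene transcription profile", and it goes on to immune function and viral biomarker levels. Primary end-point 1 is the change in ISG expression across the first injection. Secondary endpoint 1 is "Level of qHBsAg decline at treatment week 12, at end of treatment and 24 and 48 weeks off" therapy, relative to pretreatment. That endpoint is not linked to ISG.

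The Day 0 visit includes "HBV DNA , qualitative and quantitative HBeAg, HBsAg, measurements". The list for the week 2, 4, 8 and 12 visits has "TSH and quantitative HBe and HBs antigen measurement at week 12", with no quantitative test at weeks 2, 4 or 8. Table 1 agrees: quantitative HBsAg is marked at Day 0, week 12, week 24 and post-treatment week 48.

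**The concern.** A patient's HBsAg at week 12 is the Day 0 value minus whatever was lost since. If patients with low HBsAg before treatment also show a different ISG result at 6 hours, that association carries forward into every later level, even if the ISG result says nothing about who declines. Conversely, if ISG response does predict decline, the spread of baseline values acts as noise and weakens the correlation with the absolute level.

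This matters because the analysis uses every patient, however few turn out to be serological responders. It may therefore be among the better-supported mechanistic results. As planned, a positive finding would be ambiguous and a negative one would be weak evidence against a link to decline.

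**Working it through.** **The plan's own figure.** The only sample-size calculation concerns serological loss. With n = (1.960 + 0.842)² × p1(1 − p1)/(p1 − p0)² and two-sided 0.05 assumed:
- 35% v 10%: 7.849 × 0.2275/0.0625 = 28.57, so 29.
- 30% v 5%: 7.849 × 0.21/0.0625 = 26.37, so 27.

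Both stated sizes reproduce. No figure is given for the ISG-HBsAg correlation.

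**Inputs.** From the documents: n = 60 and two-sided p-values. Assumed: significance level 0.05; a true correlation of 0.4; the ratio k = SD(decline)/SD(baseline), varied from 0.125 to 1.5; decline independent of baseline.

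**Model.** Let B be Day 0 log10 HBsAg, D the decline, and Y = B − D the later level.
- ISG related to D only (correlation 0.4): |corr(ISG, Y)| = 0.4 × k/√(1 + k²).
- ISG related to B only (correlation 0.4): |corr(ISG, Y)| = 0.4 × 1/√(1 + k²).
- Power by Fisher z: Φ(atanh(r)√(n − 3) − 1.96) + Φ(−atanh(r)√(n − 3) − 1.96).

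For change from Day 0: atanh(0.4) × √57 = 0.424 × 7.550 = 3.198, and Φ(3.198 − 1.960) = 89%.

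For the level at k = 0.5, decline only: r = 0.4 × 0.447 = 0.179, z = 1.366, power 28%. Baseline only: r = 0.4 × 0.894 = 0.358, z = 2.827, significant in 81%.

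| k | corr(B, Y) | True link to decline: power using level | True link to decline: power using change | Baseline-only link: level significant |
|---|---|---|---|---|
| 0.125 | 0.99 | 7% | 89% | 89% |
| 0.25 | 0.97 | 11% | 89% | 87% |
| 0.375 | 0.94 | 19% | 89% | 84% |
| 0.5 | 0.89 | 28% | 89% | 81% |
| 0.75 | 0.80 | 46% | 89% | 71% |
| 1.0 | 0.71 | 59% | 89% | 59% |
| 1.5 | 0.55 | 74% | 89% | 40% |

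Under the baseline-only link, change or a Day 0-adjusted analysis is significant in about 5%, the nominal rate.

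**Other settings.** At k = 0.5, a true correlation of 0.3 gives 18% (level) against 65% (change), and 0.5 gives 40% against 99%. In one HBeAg group (n = 30, correlation 0.4), change has 60% power and the level 6-16% for k from 0.125 to 0.5.

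**Allowing for HBsAg loss.** A simulation (1,500 runs per setting, rank correlation, n = 60, baseline SD 0.8 log10, decline SD 0.2-0.5) added a subset whose HBsAg becomes undetectable. A true ISG-decline correlation of 0.4 gave:
- No loss: level 10-35%; rank correlation adjusted for Day 0, 76-83%.
- 10% loss: level 26-48%; change 85-87%. A baseline-only link was significant on the level in 54-68%.
- 30% loss: level 51-62%; change 80-84%; rank correlation adjusted for Day 0, 64-71%. A baseline-only link was significant on the level in 26-32%, against 5-6% with change and 4% with adjustment.

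**The case against.** The strongest reply is that the plan states its hypothesis in terms of levels, and correlating ISG with levels tests that. This stands as a reading of the sentence, so low power for decline is not a failure to do what the sentence says. But if levels alone were the question, the matching measurement would be HBsAg on Day 0, the day of the 6-hour biopsy, and that is the value left out. Three later values invite an interpretation about what follows the injection, which they cannot support alone.

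The second reply is that the size is unknown, and this also stands. A reader might infer that the planned correlation mostly repeats baseline and has little power for decline whatever happens. The documents do not support that: it needs decline to vary clearly less than baseline, with a ratio of roughly 0.5 or below. At a ratio of 1 the two influences are equal, and above it decline dominates. The design targets 30% HBsAg loss in HBeAg-negative patients; loss near that level by week 24 would narrow the gap considerably.

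Two other tempting readings fail. Day 0 HBsAg is not ignored throughout the plan: secondary endpoint 1 measures decline from pretreatment and secondary endpoint 3 uses the initial value. Nor is this about a spurious treatment effect: the study has one arm, and even a correlation with decline would not establish one.

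Finally, this correlation is not a numbered endpoint, and Analysis methodology promises a more detailed SAP. That lowers the stakes, but the promised document is not available to show that the point is covered. The n = 60 figures also ignore the planned stratification. With the 29 + 27 = 56 patients of the power calculation, change would have Φ(0.424 × √53 − 1.960) = 87% power, which alters little.

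**Conclusion.** The point holds in a limited form. The planned correlation cannot separate an association that existed before the first dose from a link between ISG response and HBsAg decline. In every setting computed, the absolute level had less power for decline than an analysis using Day 0, and it turned a purely baseline association into a significant result more often.

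How much this matters depends on quantities the documents do not give: the two SDs, their dependence, and the true correlation. The loss is severe when declines are small relative to baseline spread, and moderate when many patients lose HBsAg. This is a worthwhile, nearly free improvement to a mechanistic analysis. It does not affect the numbered endpoints.

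**What to change.** In the Analysis plan, replace the sentence with wording to this effect:

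> The ISG result will be related to log10 quantitative HBsAg at weeks 12 and 24, adjusted for Day 0 log10 HBsAg and HBeAg group. Undetectable HBsAg will be set to the assay limit, or a rank-based partial correlation will be used. Unadjusted correlations with HBsAg level are descriptive.

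Change from Day 0 with the same adjustment is an acceptable alternative. The adjustment should stay even with change, because decline may itself depend on the starting level. HBeAg group belongs in the model because the trial pools two groups, and any difference between them in both ISG and HBsAg would create a correlation. The plan should also say whether the ISG result means the 6-hour value or the difference between biopsies; the present sentence can be read either way.

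Week 4 must be reconciled with the schedule: either measure it from stored serum or drop it from this analysis. The section on research use and storage of samples provides ten to eleven aliquots per patient for quantitative HBsAg, more than the four time points in Table 1, so wider testing may be intended but should be stated. Because the Screening and sample-storage sections name different manufacturers for this test, the plan should name one assay for all values and its limit.

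The cost is wording in the detailed SAP, before data analysis. Day 0, week 12 and week 24 values and HBeAg status are already collected. No extra patients, visits or blood draws are needed; keeping week 4 costs one assay per stored sample.

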22 performed by an expert hepatopathologist blinded to the clinical information using the modified
23 Ishak scoring system. This includes the histological activity index (HAI) for inflammation and
24 necrosis (scores ranging from 0 to 18). Fibrosis will be staged using the Ishak scoring system (0-
25 6, 0=no fibrosis, 6=cirrhosis). Slides will also be immunostained for HBsAg, HbcAg, and HDV
26 antigen by peroxidase-antiperoxidase techniques and scored as 0, 1, 2 or 3+ based upon the
27 percent of cells reactive for each viral antigen (0=none, 1=10%, 2=11% to 50% and 3= \geq 51% of
28 hepatocytes).

29 Liver-infiltrating lymphocytes will be assessed for frequency and function of NK cells. m-RNA
30 levels of ISG's, immune cell markers and chemokines/cytokines will be quantitated by real-time
31 PCR or nanostring. Intrahepatic pregenomic and cccDNA will also be quantitated by Southern
32 blotting or real-time PCR.

33
34 The following will be obtained on admission:

- 35 1) Brief clinical evaluation
- 36 2) Review patient's eligibility for study

- 1 3) Symptom questionnaire
- 2 4) Visual analogue scale
- 3 5) Fatigue questionnaire (Promise 7)
- 4 6) Abdominal ultrasound, CXR and 12 lead ECG (if not done within previous 6 months)
- 5 7) Chemistry 20 (sodium, chloride, potassium, bicarbonate, calcium, phosphate, magnesium,
- 6 glucose, blood urine nitrogen, creatinine, uric acid, ALT, AST, LDH, CPK, Alkaline
- 7 Phosphatase, total and direct bilirubin, albumin, total protein), CBC (hematocrit, hemoglobin,
- 8 white blood cell count and differential, platelet count).
- 9 8) HBV DNA viral load, qualitative and quantitative HBeAg and HBsAg measurement
- 10 9) 50 mL of blood in heparinized green top tubes for NK and T cell analysis.
- 11 10) Blood sample for storage (5 mL of blood separated into serum and stored frozen in 0.5-1.0
- 12 mL aliquots)
- 13 11) Liver biopsy cut into four sections, one (at least 1.5 cm) placed in formalin for routine light
- 14 microscopy and the other 3 (.3cm, .5cm and 1 cm) placed in RNA later and flash frozen in
- 15 liquid nitrogen 24 hours later for RNA and protein analyses and flow cytometry. A liver
- 16 biopsy fragment of > 5 mm will be used to assess the frequency and function of NK cells.
- 17 12) Discharge from hospital

18

19

20 **Initiation of Treatment**

21

22 Patients will be stratified on the basis of HBeAg status into 2 groups of 30 patients each, to receive

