 5 CPK, Alkaline Phosphatase, total and direct bilirubin, albumin, total protein), CBC
 6 (hematocrit, hemoglobin, white blood cell count and differential, platelet count).
 7 6) Extended blood panel: alpha fetoprotein, gGT, immunoglobulins, rheumatoid factor, ANA,
 8 SMA, lipid panel, INR, reticulocyte count, ESR.
 9 7) 50 mL of blood in heparinized green top tubes for NK and T cell analysis.
 10 8) HBV DNA viral load, HBeAg, anti HBe, HBsAg, and anti HBs levels and quantitative HBe and
 11 HBs measurement
 12 9) Blood sample for storage (10 mL of serum and 10 ml of plasma stored frozen in 0.5-1.0 mL
 13 aliquots)
 14 10) Fibroscan
 15

16 **Table 1: List of study related procedures**
 17

Procedure	Screen	Pre-Rx biopsy	Day 0	Wk 2, 4, 8	Wk 12	Week 24 End of Rx	Post-Rx wk 12, 24, 36	Post-Rx wk 48, End of Study
H&P/breif clinical evaluation, compliance, AE, concomit. drugs, etc	X	X	X	X	X	X	X	X
Symptom questionnaire	X	X	X	X	X	X	X	X
Visual Analog Scale	X	X	X	X	X	X	X	X
Promis 7	X	X	X	wk 2		X		X
Chem 20	X	X	X	X	X	X	X	X
CBC	X	X	X	X	X	X	X	X
Anti-HAV	X							
HBsAg	X	X	X	X	X	X	X	X
HBsAg quantitative			X		X	X		X
anti-HBs	X							
HBeAg	X	X	X	X	X	X	X	X
HBeAg quantitative			X		X	X		X
anti-HBe	X							
anti-HBc	X							

anti-HCV	X							
IL28B	X							
HBV DNA	X	X	X	X	X	X	X	X
AFP	X							X
gGT	X							X
Immunoglobulins	X							X
rheumatoid factor	X							X
ANA	X							X
SMA	X							X
Lipid panel	X							X
thyroid panel	X				TSH	TSH		
INR	X							X
reticulocyte	X							X
ESR	X							X
storage - 5mL serum and 5mL plasma	S&P	Serum	Serum	S&P	S&P	S&P	S&P	S&P
Immunology - 50mL	X	X	X	X	X	X		X
Urine pregnancy	X		X	X	X	X		
UA	X					X		
Urine creatinine, phosphate, beta-2-microglobulin						X		
Liver Biopsy		X	Time d					
Abdominal u/s		X						
CXR		X						
EKG		X						
Fibroscan	X							X

1

2

3

4

5

ASSESSMENT OF RESPONSE

6

Clinical Definitions

7

8

a) **Loss of HBeAg (HBeAg-positive patients only):** loss of detectable HBeAg with or without anti-HBe seroconversion confirmed on 2 consecutive visits at least 12 weeks apart.

9

10

b) **Loss of HBsAg:** Loss of HBsAg, with or without anti HBs seroconversion confirmed on 2 consecutive visits at least 12 weeks apart.

11

- 1 c) **Sustained response:** virological, serological, biochemical, or combined response present at
2 the time of last observation and at least six months after stopping therapy.

3

4

5 The primary goals of this study are centered on understanding the mechanisms, and identification of

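### The pooled responder comparison of ISG and NK change has no HBeAg-group term, so a difference between the two enrolment groups can appear as a response effect

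*Combined protocol and SAP*

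**What the plan says.** Enrolment is by HBeAg group. The Initiation of Treatment section states: "Patients will be stratified on the basis of HBeAg status into 2 groups of 30 patients each".

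Primary end-point 1 carries no such split. It begins "The primary end-point for this study will be the change in level of ISG expression and NK cell" and continues "responses before and after 1st peginterferon injection in responders versus non-responders". Primary end-points 2 to 4, by contrast, are each confined to one HBeAg group.

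Under Statistical Analysis, the Analysis plan relates the ISG result of the 6-hour biopsy to "off-peginterferon serological outcome (HBeAg loss/seroconversion and HBsAg loss"), and separately to HBsAg levels. It then says that the "analyses will be stratified by HBV genotype and duration of NUC therapy". This sentence follows two ISG analyses; the section describes no NK analysis.

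HBeAg status is also absent from the variables listed for association with serological response. The gene-list steps under Analysis methodology group patients by relapse and/or cirrhosis. For comparing means, the only test named is Student's t-test.

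Under Clinical Definitions, one of the two routes to response is open to one group only: "Loss of HBeAg (HBeAg-positive patients only"). HBeAg-negative patients can respond only by losing HBsAg.

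**The concern.** Responder status and HBeAg group are linked by definition, because the two groups qualify as responders through different events. If the groups respond at different rates, one group is over-represented among responders. If the groups also differ in how ISG expression or NK function changes after the first injection, for reasons unrelated to response, the pooled comparison picks up part of that difference.

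Both conditions are needed. If either is absent, there is no bias.

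At stake is the main mechanistic question, for which each patient has two liver biopsies. A pooled ISG or NK difference could be read as a mechanism of response when it partly reflects HBeAg status. The same applies to the correlation of ISG with HBsAg levels if both quantities differ by HBeAg group.

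**Working it through.** **The plan's own figure.** The documents give no figure for the responder analysis. The response rates used below come from the Power calculation, so I first checked that they reproduce its sample sizes. With a one-sample comparison against a fixed rate, variance at the target rate, and two-sided alpha 0.05 (assumed; the section does not state alpha):

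n = (1.960 + 0.842)² × p₁(1 − p₁) / (p₁ − p₀)²

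- HBeAg loss, 35% against 10%: 7.849 × 0.2275 / 0.0625 = 28.57, rounded up to 29.
- HBsAg loss, 30% against 5%: 7.849 × 0.21 / 0.0625 = 26.37, rounded up to 27.

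Both match the plan.

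**Inputs for the confounding check.**

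- Group sizes: 30 + 30 (Initiation of Treatment).
- Response rates, HBeAg-positive / HBeAg-negative: 35%/30% are the planned targets. 35%/10% and 35%/5% pair the HBeAg-positive target with low rates; 10% and 5% appear in the Power calculation as rates without peginterferon. 19%/60% are two published rates in the Background: HBeAg seroconversion in the trial with a 24-week entecavir lead-in, and HBsAg loss in the small pilot study.
- HBeAg-group difference in ISG or NK change, δ: not in the documents. Assumed at 0.2, 0.5 and 0.8 SD.
- True effect of response within each group: zero.

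**Formula.** With equal groups and response rates p₁ (HBeAg-positive) and p₂ (HBeAg-negative):

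- HBeAg-positive share of responders = p₁ / (p₁ + p₂)
- HBeAg-positive share of non-responders = (1 − p₁) / (2 − p₁ − p₂)
- Spurious responder difference = δ × (first share − second share)

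For 35%/30%: 0.35/0.65 = 0.538; 0.65/1.35 = 0.481; the difference is 0.057. At δ = 0.8 SD the spurious difference is 0.057 × 0.8 = 0.05 SD.

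False-positive rates are from simulation (40,000 runs per cell, normal data, two-sided 5% Student's t-test, runs with fewer than two patients in either class dropped).

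| Rates | Share, responders | Share, non-responders | Difference | Spurious difference (SD) at δ = 0.2 / 0.5 / 0.8 | False positives at δ = 0.2 / 0.5 / 0.8 |
|---|---|---|---|---|---|
| 35%/30% | 0.538 | 0.481 | 0.057 | 0.01 / 0.03 / 0.05 | 5% / 5% / 5% |
| 35%/10% | 0.778 | 0.419 | 0.358 | 0.07 / 0.18 / 0.29 | 5% / 9% / 13% |
| 35%/5% | 0.875 | 0.406 | 0.469 | 0.09 / 0.23 / 0.38 | 6% / 11% / 19% |
| 19%/60% | 0.241 | 0.669 | −0.429 | −0.09 / −0.21 / −0.34 | 6% / 12% / 23% |

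Smaller simulations of the same cells differ from these by a percentage point or two. With HBeAg group in a linear model beside response, the false-positive rate is about 5% in every cell and the spurious difference is essentially zero.

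**The case against.** - **The effect is negligible at the plan's own rates.** This stands. At 35% and 30% the leak is at most 0.05 SD over the range examined.
- **The larger figures need rates the plan does not predict.** This largely stands. The 10% and 5% are assumed rates without peginterferon. The 19% and 60% come from different outcomes and settings: the first is seroconversion at the end of treatment after a short lead-in, the second is from a small pilot. They show that equal rates cannot be taken for granted; they do not forecast unequal ones.
- **No document gives a group difference in ISG or NK change.** This stands, which is why a range is shown. A reader might infer from aim 4 that the sponsor expects the groups to differ in this respect. Aim 4 reads "To determine if there are differences in epigenetic regulation of cccDNA between HBeAg positive and negative CHB at baseline", continuing to the time after the first dose. It asks whether a difference exists, concerns cccDNA epigenetics, and does not mention ISG or NK response.
- **Pooling is inferred.** This partly stands. End-point 1 reads as pooled but does not say so. If HBeAg loss is analysed as a separate outcome, it lies within one group and cannot be confounded by group. The problem then remains for HBsAg loss and for the correlation with HBsAg levels. The plan does not say which reading applies.
- **A more detailed statistical analysis plan is promised before data analysis.** True, and it is the natural place for the change. It does not answer the point, since the present text already names its stratifiers and omits this one.

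**Conclusion.** The omission is real, and its consequence is conditional. A spurious response effect needs three things together: a pooled responder contrast, different response rates by HBeAg group, and a group difference in ISG or NK change. At the planned rates the false-positive rate remains about 5-6%. At clearly unequal rates it is about 5-6% for an assumed 0.2 SD difference, 9-12% for 0.5 SD and 13-23% for 0.8 SD.

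Two stronger readings are not supported. One is that the primary result will be confounded: the documents establish neither unequal rates nor a group difference in ISG or NK change. The other is that the NK analysis is stratified by genotype and treatment duration with HBeAg group left out: the stratification sentence covers the ISG analyses, and no NK analysis is written.

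The change is still worth making, because the term is known for every patient and protects the main comparison at almost no cost.

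**What to change.** Keep the existing stratification sentence and add, there or in the promised detailed plan:

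> *The pooled responder versus non-responder analyses of ISG and NK change, and the correlation of ISG with HBsAg levels, will include HBeAg group as a covariate. Response is loss of HBeAg and/or HBsAg in HBeAg-positive patients, and HBsAg loss in HBeAg-negative patients. Analyses of HBeAg loss alone are confined to HBeAg-positive patients. Within-group estimates are descriptive where responders are few.*

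The response definition keeps HBsAg loss as a route to response in HBeAg-positive patients, in line with the hypothesis under On-treatment liver biopsy and with primary end-point 3.

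A covariate is preferable to a further full stratum. At the planned rates about 30 × 0.35 + 30 × 0.30 = 19.5 responders are expected, and crossing HBeAg group with genotype and treatment duration would leave sparse cells. The caution on within-group estimates is needed because a 5% rate in 30 HBeAg-negative patients gives 1.5 expected responders and a 0.95³⁰ = 21% chance of none.

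The cost is one degree of freedom and a few lines of text. In a check with a true 0.8 SD response effect, planned rates and an assumed 1 SD group difference, power was about 80% with the term and 77% without it.
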